#### 9.2.2. Ancillary Data

Data managed by a central vendor will be stored electronically in the central laboratory's database system. Data will subsequently be transferred from the central vendor to the Lilly generic labs system.

Bioanalytical data will be stored electronically in the bioanalytical laboratory's database. Data will subsequently be transferred from the bioanalytical laboratory to the Lilly generic labs system.

Data from complaint forms submitted to Lilly will be encoded and stored in the global product complaint management system.

## 10. Data Analyses

For this study, approximately 40 patients will be enrolled. Patients with prostate cancer will be treated at 1 of 2 dosages of LY3022855, and patients with breast cancer will be treated at 1 of 4 dosages of LY3022855. Of those enrolled patients, approximately 36 patients will be evaluable: 30 patients with advanced, refractory breast cancer and 6 patients with advanced, refractory prostate cancer. Refer to Section 6.1 for the definition of an evaluable patient.

CSF-1 is the primary pharmacodynamic biomarker documented in Study JSCA. Serum CSF-1 was quantified for 17 patients over time; that is, at baseline and 8 hours after the first infusion. All those patients had increased levels of CSF-1 at 8 hours, compared with the baseline level. The effect size (or Cohen's  $d$ ) is 5.81. Consequently, the power of observing any change between the eighth hour and baseline is close to 1 as long as the number of samples is  $\geq 3$ .

However, when the effect size is as small as 1 for the pharmacodynamic markers other than CSF-1, the power is approximately 0.159 if only 3 patients are sampled.

For Dosages C and D (patients with breast cancer), the sample size of 10 for each dosage provides a reasonable power to explore preliminary signals of efficacy. Assuming that a true best overall response rate (ORR) less than 20% indicates inadequate antitumor activity, then at a one-sided type 1 error rate of 5%, the total sample size of 10 will provide 80% power if the true best ORR is 60% or higher, using a 2-stage design method as follows. During the first stage, 5 patients will be enrolled and treated on each of Dosages C and D. If 2 or more of the 5 patients on either dosage (C or D) are observed to be responders by the end of the first stage, an additional 5 patients will be enrolled at the applicable dosage. Then, if 5 or more of the total of 10 patients at that dosage are observed to be responders by the end of the second stage, further exploration of drug efficacy is warranted for that dosage.

All data collected will be summarized using descriptive statistics or graphics, if appropriate, and will also be listed.

### 10.1. General Considerations

Statistical analysis of this study will be the responsibility of Eli Lilly and Company.

The interpretation of the study results will be the responsibility of the investigator with the Lilly CRP, pharmacokineticist, and statistician. The CRP and statistician will also be responsible for the appropriate conduct of an internal review for both the final study report and any study-related material to be authorized by Lilly for publication.

## 10.2. Patient Disposition

All patient discontinuations will be documented, and the extent of each patient's participation in the study will be reported. If known, a reason for their discontinuation will be given.

A summary of the number and percentage of patients entered into the study, enrolled in the study, and treated, as well as number and percentage of patients discontinuing (overall and by reason for discontinuation), will be provided.

A summary of all important protocol deviations will be provided.

## 10.3. Patient Characteristics

Patient characteristics will include the following:

- Patient demographics
- Baseline disease characteristics
- ECOG performance status
- Preexisting conditions
- Historical illnesses
- Prior disease-related therapies (including information on best response and time to progressive disease)
- Concomitant medications

Other patient characteristics will be summarized as deemed appropriate.

## 10.4. Safety Analyses

All patients who receive at least one dose of LY3022855 will be evaluated for safety and toxicity. Adverse event terms and severity grades will be assigned by the investigator using CTCAE v4.0.

All safety summaries and analyses will be based upon the Safety Population, defined as all enrolled patients who have received at least one dose of study drug.

Overall exposure to study drug, the numbers of patients completing each cycle, and the dose intensity will be summarized using descriptive statistics.

An overall summary will be provided for AEs deemed by the investigator to be possibly related to study medication, and repeated for events regardless of study drug causality.

The number of evaluable patients who experienced a TEAE, an SAE, or an AE related to study drug, or who died or discontinued from the study due to an AE will be summarized.

Reasons for death will be summarized separately for on-therapy and within 30 days after last dose of study drug.

Laboratory results will be classified according to CTCAE v4.0. Laboratory results not corresponding to a CTCAE v4.0 grade will not be graded.

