### 7.6.1. *Evaluable Patients*

Patients who withdraw from the study before receiving study drug(s) will be replaced and will not be included in the safety or efficacy assessments. Safety analyses will be conducted on all patients who have received at least one dose of study drug, regardless of whether they are deemed evaluable for the assessment of a dose level.

Any patient who does not complete 1 cycle of LY3022855 treatment, undergo 1 baseline and 1 posttreatment tumor biopsy procedure (ie, attempted, whether the biopsy is successful or not), and complete immune blood studies for 1 cycle will be deemed nonevaluable for assessment of a dose level.

Patients who complete 1 cycle of LY3022855 treatment, undergo 1 baseline and 1 posttreatment tumor biopsy procedure (ie, attempted, whether the biopsy is successful or not), and complete immune blood studies for 1 cycle will be considered evaluable for the assessment of a dose level. Nonevaluable patients may be replaced to ensure that 36 evaluable patients are attained.

Patients who complete 1 cycle of therapy but, for whatever reason, are not evaluable for PK may be replaced upon consultation with the investigator(s) and the Lilly CRP or CRS to ensure adequate PK data.

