6.1. General Considerations

Statistical analysis of this study will be the responsibility of the sponsor. The analyses for this study will be descriptive, except for exploratory analyses of biomarker data, as deemed appropriate. Analyses of the biomarker data will be described in a separate biomarker SAP.

Data analyses will be provided by cancer type, dose group, and for all study patients combined, wherever appropriate. For continuous variables, summary statistics will include number of patients, mean, median, standard deviation, minimum, and maximum. Categorical endpoints will be summarized using number of patients, frequency, and percentages.

The following data handling conventions will be used in the analysis (see [Table 6.1](#)).

Table 6.1. Data Handling Conventions

Term	Definition or Rule
Relative Study Day	If assessment is on or after date of first dose then (date of assessment) – (date of first study drug dose) +1
	If assessment precedes first dose of drug then (date of assessment) – (date of first study drug dose)
	There is no study day 0. Study day 1 is the date of first dose and study day -1 is the day before the first dose.
Baseline	For change from baseline analyses, baseline value is defined as the last reported measure on or before the first dose date (prior to the dose administration), unless, otherwise, specified. For change from baseline within a cycle, baseline value is defined as the measure prior to the first dose of that cycle, unless, otherwise, specified.
Entered	Patients who have signed the informed consent document directly.
Enrolled population	Patients who have been assigned to study treatment and have received at least 1 dose of any study treatment.
Screen Failures	Patients who have signed informed consent, do not meet eligibility criteria and are not enrolled.
Evaluable population	Patients who complete 1 cycle of LY3022855 treatment, undergo 1 baseline and 1 posttreatment tumor biopsy procedure, and complete immune blood studies for 1 cycle
Safety Population	Patients who have received at least 1 dose of study drug.

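### Protocol 10.4 counts its adverse-event overview in evaluable patients, against its own rule that safety summaries use every dosed patient (minor)

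*Protocol*

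**What the plan says.** Protocol 10.4 opens by stating that all dosed patients are assessed for safety and toxicity, and then fixes the analysis set: "All safety summaries and analyses will be based upon the Safety Population, defined as all enrolled patients who have received at least one dose". Three paragraphs later comes the overview of treatment-emergent events, serious events, related events, deaths and adverse-event discontinuations: "The number of evaluable patients who experienced a TEAE, an SAE, or an AE related to study drug, or who died or discontinued". The sentence after that, on reasons for death, has no such restriction: "Reasons for death will be summarized separately for on-therapy and within 30 days after last dose of study drug".

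Protocol 7.6.1 deals with the relation between safety and evaluability directly: "Safety analyses will be conducted on all patients who have received at least one dose of study drug", and it adds that this holds "regardless of whether they are deemed evaluable for the assessment of a dose level".

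SAP Table 6.1 (Section 6.1) lists the evaluable and safety populations as separate entries. The evaluable population is "Patients who complete 1 cycle of LY3022855 treatment, undergo 1 baseline and 1 posttreatment tumor biopsy procedure, and complete immune blood studies for 1 cycle". The Safety Population needs only one dose. The enrolled population is "Patients who have been assigned to study treatment and have received at least 1 dose of any study treatment", so an enrolled patient is by definition a dosed patient.

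SAP 6.9.2 also starts from all dosed patients. Its overview sentence covers treatment-emergent events, serious events and possibly related treatment-emergent events. It refers simply to patients, without the word *evaluable*.

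**The concern.** Two sentences of the same section name different populations for the same output, and both cannot be followed.

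*Evaluable* cannot be read loosely as evaluable for safety. Protocol Section 10 points to Section 6.1 for its meaning, and neither document defines a safety-evaluable set. The definition depends on reaching the end of Cycle 1 (at least Day 43) and on procedures that serve the pharmacodynamic objective. A patient who dies or stops for an adverse event before then fails it automatically. For example, Protocol 6.3.1 and 7.2.1.1 require permanent discontinuation after a Grade 3 or 4 infusion-related reaction. If that happened at the first infusion, the patient would be non-evaluable, and the literal overview would omit both the event and the discontinuation.

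Safety is a secondary objective. At stake is an overview from which the earliest and most consequential events are removed by construction, in a report whose other tables include them.

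**Working it through.** The plan gives no power, sample-size or alpha figure to reproduce on this point. The check is a comparison of population rules, followed by simple arithmetic for scale.

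**1. The rules side by side**

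| Place | Population for safety |
|---|---|
| Protocol 10.4, opening and general rule | All patients with at least one dose |
| Protocol 10.4, overview sentence | Evaluable patients |
| Protocol 10.4, reasons for death | No evaluability restriction |
| Protocol 7.6.1 | All dosed patients, evaluable or not |
| SAP 6.9.2, opening | All patients with at least one dose |
| SAP 6.9.2, overview sentence | Patients, without *evaluable* |
| SAP 6.9.3 | All deaths on study |

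Only the 10.4 overview sentence is out of line. It is current text: the Attachment 11 entry for 10.4 shows only the opening paragraph and no change to this sentence.

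**2. Where the SAP settles it and where it does not**

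The SAP 6.9.2 overview sentence includes neither deaths nor discontinuations due to an adverse event. For the combined count, the 10.4 sentence is the only direct specification. For those two items the intended population has to come from Protocol 7.6.1 and the general rule in 10.4.

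**3. Scale on planned numbers**

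Inputs from Protocol Section 10: about 40 enrolled, hence dosed; "Of those enrolled patients, approximately 36 patients will be evaluable", made up of 30 breast + 6 prostate = 36.

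- Dosed but not evaluable: 40 − 36 = 4
- Share of dosed patients: 4/40 = 10%

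**4. Illustration of the selection effect**

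The documents give no rate of early death or early adverse-event discontinuation, so the event counts here are assumptions. Let m be the number of patients with such an event before completing Cycle 1 (all non-evaluable) and L the number with a later one (all evaluable). I also assume that the literal reading restricts the denominator to evaluable patients.

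Safety Population rate = (m + L)/40. Evaluable-only rate = L/36.

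| m | L | Safety Population | Evaluable only |
|---|---|---|---|
| 0 | 2 | 2/40 = 5.0% | 2/36 = 5.6% |
| 2 | 2 | 4/40 = 10.0% | 2/36 = 5.6% |
| 4 | 2 | 6/40 = 15.0% | 2/36 = 5.6% |
| 4 | 0 | 4/40 = 10.0% | 0/36 = 0.0% |

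The evaluable-only figure does not move with m, because Cycle 1 events cannot enter it.

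**The case against.** The strongest reply is that the documents already resolve the conflict. Section 10.4 states the all-dosed rule twice before the stray word, Protocol 7.6.1 excludes an evaluability filter expressly, and the SAP, written for this protocol version, does not carry the word into its adverse-event section. A programmer would have to overlook all of that to produce the wrong table. This stands, and it is why the point is minor. It does not remove the error: for the combined count with deaths and discontinuations there is no parallel SAP sentence, so the faulty one is the only direct instruction.

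A second reply is that the events appear elsewhere, and this also stands. Protocol 10.2 reports discontinuations overall and by reason. SAP 6.3 summarizes reasons for stopping treatment and leaving the study. SAP 6.9.3 lists and summarizes deaths. SAP 6.12 lists deaths and adverse-event discontinuations by reporting period, and SAP 6.13 gives registry adverse-event counts and participant flow. No event would vanish from the report; the overview would simply disagree with these outputs.

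A third reply is that 10% is not an impact estimate. That is right. The 36 is a completion target that can be reached by replacing non-evaluable patients, so the number left out is not capped at 4. Both totals also assume that Dosages C and D expand from 5 to 10 patients each. If neither does, planned evaluable breast patients fall to 30 − 10 = 20 and the evaluable total to 36 − 10 = 26. The figure of 4 in 40 shows only the order of magnitude in the plan.

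**Conclusion.** The concern holds, as a minor one. Protocol 10.4 contradicts itself, and its overview sentence, as written, states a wrong analysis rule: it conditions a count of deaths and adverse-event discontinuations on having completed Cycle 1. The word is probably a leftover, since every other relevant statement points to all dosed patients.

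On planned figures the literal wording leaves out about 4 of 40 dosed patients. How many events that would omit cannot be derived from the documents, and the rates illustrated above rest on assumed counts. The consequence is confined to one overview table. The primary objective, the two-stage response rule and the collection of safety data are unaffected.

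**What to change.** In Protocol 10.4, replace *evaluable patients* in the overview sentence with *patients in the Safety Population*. This applies the rule the section already states.

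Optionally, in the same edit, name the Safety Population as the denominator in SAP 6.9.2. Adverse-event discontinuations could be added to that overview on the same population, so that the SAP covers the item 10.4 promises.

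The required change is a one-phrase correction, with no new data, outputs or analyses. The optional SAP additions are a line or two and use data already collected.

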## 10.5. Pharmacokinetic Analyses

Pharmacokinetic analyses will be conducted on patients who have received at least one dose of the study drug and have had samples collected, and PK serum concentrations of LY3022855 will be determined.

The parameters for analysis will include but not be limited to maximum concentration ( $C_{max}$ ) and trough concentration ( $C_{trough}$ ) of LY3022855. Additional analyses will be performed if warranted by data, and other validated PK software programs (for example, NONMEM) may be used if appropriate and approved by Global Pharmacokinetic management. The version of any software used for the analysis will be documented and the program will meet the Lilly requirements of software validation.

## 10.6. Pharmacodynamic Analyses

Pharmacodynamic data from all patients undergoing pharmacodynamic assessments will be analyzed.

To study the impact of the study drug and the dose levels on the patients, the changes from baseline over time in peripheral blood immune cell subsets will be documented. The immunomodulatory activity of LY3022855 will be documented by examining markers that include, but are not limited to: Live-Dead, CD3, CD4, CD8, CD14, CD16, FoxP3, PD-1, Ki-67, CTLA-4, TIM-3, LAG-3, and ICOS. The expression of those markers will be quantified by flow cytometric analysis with an antibody panel.

In addition, changes from baseline over time in serum cytokines will be determined by MSD multiplex cytokine immunoassay or ELISA. The markers to be measured using these technologies include, but are not limited to: CSF-1, IFN- $\gamma$ , IL-1 $\beta$ , IL-2, IL-4, IL-6, IL-8, IL-10, IL-12p70, IL-13, IL-34, and TNF- $\alpha$ .

Biomarker measures of protein expression, based on flow cytometry, MSD, and ELISA, will be summarized by tumor type and/or dosage, based on enrolled patients. Summary statistics may include means, medians, corresponding standard errors, quartiles, and ranges. Graphics, including profile plots of markers over time, will be generated to explore potential patterns between patients. Correlation analyses between biomarkers and relative laboratory tests may be performed to further explore the activity of LY3022855.

## 10.7. Pharmacokinetic/Pharmacodynamic Analyses

An exploratory correlative analysis of LY3022855 PK and pharmacodynamics may be conducted.

## 10.8. Efficacy Analyses

Tumor response data will be reported using listings and descriptive statistics. The ORR is estimated by the proportion of enrolled patients who have a best overall response of complete response (CR) or partial response (PR). The disease control rate (DCR) is estimated by the proportion of enrolled patients who have a best overall response of CR, PR, or stable disease. A 95% exact confidence interval will be constructed to determine the level of precision of the ORR and DCR if appropriate. Time-to-event variables such as progression-free survival (PFS), duration of response, and overall survival (OS) will be tabulated if appropriate. The Kaplan-Meier method (Kaplan and Meier 1958) will be used to estimate the survival curves, medians, and survival rates at specified time points, if applicable.

